Treatment of Outliers during Pharmacokinetic Analysis

Application of this procedure to all PK analyses is not a requirement. Rather, this procedure provides justification for exclusion of data when scientifically appropriate. This procedure describes the methodology for identifying an individual value as an outlier for potential exclusion, but does not require that the value be excluded from analysis. The following methodology will not be used to exclude complete profiles from analysis.

Data within an Individual Profile

A value within an individual profile may be excluded from analysis if any of the following criteria are met:

- For PK profiles during single dosing of non-endogenous compounds, the concentration in a pre-dose sample is quantifiable.
- For any questionable datum that does not satisfy the above criteria, the profile will be evaluated and results reported with and without the suspected datum.

Data between Individual Profiles

1. If $n < 6$, then the dataset is too small to conduct a reliable range test. Data will be analyzed with and without the atypical value, and both sets of results will be reported.
2. If $n \geq 6$, then an objective outlier test will be used to compare the atypical value to other values included in that calculation:
 - a. Transform all values in the calculation to the logarithmic domain.
 - b. Find the most extreme value from the arithmetic mean of the log transformed values and exclude that value from the dataset.
 - c. Calculate the lower and upper bounds of the range defined by the arithmetic mean $\pm 3 \times \text{SD}$ of the remaining log-transformed values.
 - d. If the extreme value is within the range of arithmetic mean $\pm 3 \times \text{SD}$, then it is not an outlier and will be retained in the dataset.
 - e. If the extreme value is outside the range of arithmetic mean $\pm 3 \times \text{SD}$, then it is an outlier and will be excluded from analysis.

If the remaining dataset contains another atypical datum suspected to be an outlier and $n \geq 6$ following the exclusion, then repeat step 2 above. This evaluation may be repeated as many times as necessary, excluding only one suspected outlier in each iteration, until all data remaining in the dataset fall within the range of arithmetic mean $\pm 3 \times \text{SD}$ of the log-transformed values.

Reporting of Excluded Values

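### The between-profile outlier test uses an uncalibrated 3 SD bound: if applied, it would flag a valid value in about 18–21% of clean data sets at the planned sizes

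*SAP*

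**What the plan says.** The rule is in SAP section 9.3.1, under the heading on treatment of outliers, part on data between individual profiles.

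- Below six values, results are reported with and without the atypical value. From six upward, "an objective outlier test will be used to compare the atypical value to other values included in that calculation".
- After log transformation, step 2b reads "Find the most extreme value from the arithmetic mean of the log transformed values and exclude that value from the dataset".
- Step 2c sets the bound as the "arithmetic mean $\pm 3 \times \text{SD}$ of the remaining log-transformed values". The multiplier does not depend on n, and no error rate is stated.
- Under step 2e, if the value lies outside the bound, "then it is an outlier and will be excluded from analysis".
- If another suspect value remains and n is still at least 6, "This evaluation may be repeated as many times as necessary, excluding only one suspected outlier in each iteration".

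The preamble to the same procedure is softer: "Application of this procedure to all PK analyses is not a requirement", and the method identifies a value for possible exclusion "but does not require that the value be excluded from analysis". Excluded values must be documented in the final report. With-and-without reporting is not required at n of 6 or more.

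Section 9.1 describes AUCs and Cmax as log-normal. Section 7 plans about 42 enrolled and at least 28 completers. Section 9.3.2 analyses log AUC(0-τ) and log Cmax of three analytes by paired t-test with a 90% CI.

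**The concern.** A 3 SD limit looks strict because a single normal value, chosen in advance, rarely lies that far out. Here the value is not chosen in advance. It is the largest of n deviations, and it is judged against an SD from which it has been removed. Both features make a valid extreme value look more unusual than it is, and a fixed multiplier corrects for neither.

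The preamble presents the procedure as a justification for excluding data. A test that often fires on clean data is a weak justification. The values at stake are the AUC and Cmax results that serve the primary objective. Removing a valid extreme value understates the SD and geometric CV, and in a paired analysis the loss of one treatment's value loses the whole pair.

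**Working it through.** **Inputs.** From the SAP: smallest n = 6; multiplier 3; mean and SD from the n−1 remaining log values (section 9.3.1); n = 28 completers and 42 enrolled (section 7). Assumption: clean data are normal on the log scale, in line with section 9.1. The SAP gives no false-flag rate, so there is no stated figure to reproduce.

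**False-flag rate.** For one value named in advance, (x − mean of rest) / (SD of rest × √(1 + 1/(n−1))) follows a t distribution with n−2 df, and 1 + 1/(n−1) = n/(n−1). So

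p = 2·P(t[n−2] > 3/√(n/(n−1))),

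and because the most extreme of n values is tested, the rate per data set is about n·p (an upper bound, close when p is small).

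| n | 3/√(n/(n−1)) | p | n·p | simulated |
|---|---|---|---|---|
| 6 | 3/1.0954 = 2.739 | 0.0520 | 0.312 | 0.312 |
| 28 | 3/1.0184 = 2.946 | 0.00671 | 0.188 | 0.185 |
| 42 | 3/1.0121 = 2.964 | 0.00510 | 0.214 | 0.208 |

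The last column follows steps 2a–2e on 400,000 clean data sets per n. The rate is lowest near n = 20 (0.180).

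**Where the excess comes from.** With the suspect value kept in the SD, a 3 SD limit would flag about 2.8% of clean sets at n = 28 and none at n = 6.

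**Repetition.** With the loop run as written at n = 28, about 3% of clean sets lose two or more values; the mean is about 0.23 values per set.

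**Effect on the analysis, if every flag is acted on.** The SAP does not say whether the values in the calculation are each treatment's parameters or the within-subject log ratios. These are alternatives, so their effects must not be added together.

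- *Per treatment, n = 28:* about 27–32% of comparisons lose at least one pair. Coverage of the nominal 90% CI stays near 89–90%. This assumes a between-subject CV of 30–50%, which the SAP does not give, and a within-subject CV of 14–20%, the range in section 7.
- *Within-subject log ratios:* coverage is about 88% overall, and about 77–80% among data sets in which a value was dropped (77% at n = 28, higher at n = 42).

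When the rule fires on a set of 28, the SD falls on average to 0.83 of its full-data value.

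**Calibrated multiplier.** Setting the rate per data set to 5% gives k(n) = t[1−0.05/(2n), n−2] × √(n/(n−1)):

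- n = 6: 4.851 × 1.0954 = 5.31
- n = 28: 3.480 × 1.0184 = 3.54
- n = 42: 3.490 × 1.0121 = 3.53

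Simulation with these multipliers returns about 5% at n = 6, 28 and 42.

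**The case against.** The strongest reply is that the SAP obliges nobody to run the test or to act on it. The preamble makes both discretionary, and step 2 starts from a value that someone already regards as atypical. A reader might infer from the rates above that the plan will throw out a valid value in nearly one data set in five. The document does not support that: these are flag rates if the test is applied, and so an upper limit on exclusions. This part of the objection stands. It does not repair the cut-off, because a flag that appears in about a fifth of clean data sets is poor evidence whenever someone relies on it. Step 2e also says a flagged value "then it is an outlier and will be excluded from analysis", which sits badly with the preamble.

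Second, n = 6 is no planned primary data set. That stands too: the figures that matter here are those for 28 to 42, and the 31% only shows what the rule permits at its lower limit.

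Third, the inferential damage is small. Per treatment, coverage hardly moves. On log ratios it falls about two points overall, and the 77–80% is conditional on the rule having fired. The SAP states no equivalence margin that this would tip. This stands as a limit on severity.

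Fourth, repetition is not open-ended. It removes one value per pass, needs at least six values, and stops once all lie inside the range. Exclusions are also documented, although no all-data result is required beside them at n of 6 or more.

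**Conclusion.** The point holds as a miscalibration of a stated rule. If applied to clean log-normal data, the test flags at least one valid value in about 18–21% of data sets at n = 28 to 42, and in about 31% at n = 6. The rates rest on log-normality; heavier tails would raise them. They bound, and do not estimate, the number of values that will be dropped.

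The likely harm is loss of valid values or pairs and understated variability, with a small loss of CI coverage whose size depends on which values are tested. It would be wrong to read the 77–80% as the coverage of the planned analysis, or to combine the lost pairs of one reading with the coverage loss of the other. The change is worth making because the affected parameters serve the primary objective and the correction is cheap.

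**What to change.** Choose one of two procedures, not both:

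1. In steps 2c–2e, replace 3 by k(n) = t[1−0.05/(2n), n−2] × √(n/(n−1)), where n is the number of values before the suspect one is removed. Update n at each pass and set a maximum number of passes in advance, for example 2.
2. Or replace step 2 by a generalised ESD test at the 5% level with the same pre-set maximum.

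State also whether the test is run on each treatment's log parameters or on within-subject log ratios.

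The 5% level is a conventional choice, not one taken from the SAP, and it applies per data set. Over 12 sets (3 analytes × 2 parameters × 2 treatments), if they were independent, the chance of some false flag would be 1 − 0.95¹² = 0.46, against 1 − 0.815¹² = 0.91 under the present rule at n = 28. A stricter level could be chosen.

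The cost is a change of SAP wording and a small change to the outlier program. The downside is that slightly fewer true anomalies are flagged automatically; these can still be excluded for a documented cause.

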7. SAMPLE SIZE JUSTIFICATION

Approximately 42 subjects will be enrolled so that a minimum of 28 subjects complete the study.

For EE area under the concentration versus time curve (AUC) and maximum observed drug concentration (C_{max}), the intra-subject variability (coefficient of variation [CV]) was estimated to be 18.2% and 14.2%, respectively (derived from study H9X-MC-GBCQ). Based on this assumption, 28 subjects will provide a precision of 0.10 and 0.08 on a log-scale for AUC and C_{max} , respectively. This would result in a 90% probability that the half-width of the 90% confidence interval (CI) of the ratio of geometric least square means for AUC and C_{max} is no larger than 9.3% and 7.3%, respectively.

For norelgestromin (NGMN) AUC and C_{max} , the intra-subject variability (CV) was estimated to be 16.3% and 20.0% respectively (derived from study H9X-MC-GBCQ). Based on this assumption, 28 subjects will provide a precision of 0.09 and 0.11 on a log-scale for AUC and C_{max} , respectively. This would result in a 90% probability that the half-width of the 90% CI of the ratio of the geometric least square means for AUC and C_{max} is no larger than 8.3% and 10.2%, respectively.

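### SAP 9.3.1 both permits and requires exclusion of a between-profile outlier, and with six or more values the all-data result need not be shown beside the reduced one

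*SAP*

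**What the plan says.** The outlier procedure is in SAP section 9.3.1, under Treatment of Outliers during Pharmacokinetic Analysis.

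- **Preamble.** Use of the procedure is optional: "this procedure provides justification for exclusion of data when scientifically appropriate". It identifies a value for possible removal "but does not require that the value be excluded from analysis". It also sets a limit: "The following methodology will not be used to exclude complete profiles from analysis".
- **Within one profile.** A questionable concentration leads to "results reported with and without the suspected datum".
- **Between profiles, fewer than six values.** No range test is run. Instead, "Data will be analyzed with and without the atypical value, and both sets of results will be reported".
- **Between profiles, six or more values.** A test is used to "compare the atypical value to other values included in that calculation". The values are logged, the most extreme is set aside, and mean ± 3 SD is computed from the rest. If the extreme value lies outside that range, "then it is an outlier and will be excluded from analysis". The step can be repeated, one value at a time.
- **Reporting of Excluded Values.** Excluded values are documented in the final report, and approval of the report counts as approval of the exclusion.

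Section 7 plans enrolment "so that a minimum of 28 subjects complete the study". Section 9.3.2 compares log AUC(0-τ) and Cmax between treatments with a paired t-test and a 90% CI. It neither invokes the outlier rule nor rules it out.

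**The concern.** Three things are left open.

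1. **Whether a flagged value is removed.** The preamble leaves it open; step 2e does not. An analyst who deletes the value and one who keeps it can both claim to have followed the SAP.
2. **What is reported.** With and without results are required for fewer than six values and for questionable data within a profile. They are not required in the branch that applies to a study of this size.
3. **What the rule applies to.** Nothing exempts AUC(0-τ) or Cmax. The bar on dropping complete profiles does not settle this, because one parameter value is not a profile. If such a value is deleted under either treatment, the subject has no pair and leaves the paired t-test.

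In an interaction study, a subject with a very large true fall in contraceptive exposure is something readers would want in the main estimate. Steps 2a to 2e look only at statistical distance, so they can remove such a subject, and the full-data ratio and 90% CI need not then appear.

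**Working it through.** **Inputs.** From SAP section 7: n = 28; within-subject CV 14.2% (EE Cmax) and 20.0% (NGMN Cmax). From 9.3.2: paired t-test on logs, 90% CI. The SAP gives no between-subject CV, so 25, 35 and 50% are assumed.

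**The plan's own figure.** With sw = √ln(1 + CV²), the log half-width not exceeded with 90% probability is t(0.95, 27) × sw × √(2/28) × √(χ²(0.90, 27)/27). This gives 0.096, 0.075, 0.086 and 0.105 for EE AUC, EE Cmax, NGMN AUC and NGMN Cmax. The SAP states 0.10, 0.08, 0.09 and 0.11, so the precision is reproduced and is not in dispute.

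**The text side by side.**

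| Case | Value removed? | Both results required? |
|---|---|---|
| Within a profile, questionable datum | may be | yes |
| Between profiles, n < 6 | no test | yes |
| Between profiles, n ≥ 6, beyond 3 SD | preamble: not required; step 2e: yes | no |

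**How often clean data would be flagged if the test were always run.** The set-aside value is compared with the other 27, so the chance per value is P(|t26| > 3/√(1 + 1/27)) = 0.0067. Times 28, this is 0.188 for one set of values (simulated: 0.182 to 0.187 by treatment). Over both treatments, about 27 to 33% of clean trials lose at least one pair.

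**Coverage on clean log-normal data.** Testing by treatment (12,000 trials per setting, Monte Carlo SE 0.003), the 90% CI covers in 0.889 to 0.898 of trials, against 0.895 to 0.904 with all data kept. If subject ratios were tested instead, coverage would be 0.875 against 0.899 (40,000 trials).

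**Why an extreme responder can be deleted.** Within-subject CV 14.2% gives a log variance of ln(1 + 0.142²) = 0.0200. Adding ln(1 + CV²) for between-subject CV 25, 35 and 50% (0.0606, 0.1156, 0.2231) gives log SDs of about 0.284, 0.368 and 0.493 within a treatment. A 70% fall is ln 0.30 = −1.204, that is 4.2, 3.3 and 2.4 SD from the centre. The chance that the value lies below −3 SD is roughly Φ(4.24 − 3), Φ(3.27 − 3) and Φ(2.44 − 3), or about 0.89, 0.61 and 0.29. Simulating the full iterated rule gives 88, 63 and 32%.

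**Effect on the ratio.** One of 28 with a 70% fall and no effect in the rest gives exp(−1.204/28) = 0.958 with all data and 1.000 without that subject. Weighting by the simulated deletion rates gives exp(−0.043 × 0.12) = 0.995, exp(−0.043 × 0.37) = 0.984 and exp(−0.043 × 0.68) = 0.971, close to the simulated values below.

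Simulated, test always run by treatment, within-subject CV 14.2%, between-subject CV 25/35/50%:

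| Subjects affected | Ratio, all data | Ratio after the rule |
|---|---|---|
| 2 of 28, 50% fall | 0.952 | 0.964 / 0.959 / 0.955 |
| 6 of 28, 70% fall | 0.773 | 0.778 to 0.779 |
| 14 of 28, 60% fall | 0.632 | unchanged within 0.001 |
| All 28, 50% fall | 0.500 | unchanged to three decimals |
| 1 of 28, 70% fall | 0.958 | about 0.996 / 0.985 / 0.972 |
| 2 of 28, 70% fall | 0.917 | 0.985 / 0.960 / 0.938 |

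For 1 of 28 with a 70% fall, the mean lower 90% limit rises from 0.870 to about 0.930, 0.913 and 0.892. For 2 of 28 with a 70% fall, it rises from 0.814 to 0.914, 0.875 and 0.842. In the latter case at within-subject CV 20.0%, the ratio goes from 0.917 to 0.978, 0.955 and 0.935.

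**The case against.** The preamble introduces the whole procedure, so it can be read as governing, with step 2e as loose wording for the mechanics once an exclusion is sought. That is a fair guess at the intent, but it is not what step 2e says. Reading use as optional and exclusion as binding once the test is run does not help either, because the preamble's release concerns the identified value itself.

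The difference between the two sample-size branches has a stated reason. Below six values the SAP considers a range test unreliable and reports both results instead; from six upward the test takes that role. This stands: the missing second result is a weakness of the rule, not a second contradiction.

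A reader might infer that the rule hides data. The SAP does not support that. Excluded values are documented, special handling is to be reported (9.3.1), all databased data are listed (9.1), and individual AUC(0-τ) and Cmax values are listed and plotted by treatment (9.3.2). A reader could recompute the full-data result; the SAP simply does not require it to be shown.

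A reader might also infer that the primary comparison is generally biased, or that about 18% of data sets per treatment would lose a value. Neither follows. Use is optional, only a value already judged atypical is tested, and 9.3.2 does not invoke the rule. The simulated rates are upper bounds. The SAP sets no no-effect bounds, so no prespecified conclusion changes.

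**Conclusion.** The point stands as a contradiction in wording plus a reporting gap. Section 9.3.1 does not fix whether a between-profile outlier is removed, and for the planned sample size it does not require the all-data ratio and 90% CI beside a reduced one.

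The numerical consequence is negligible in most settings: coverage on clean data tested by treatment is about 0.90 with or without the rule, and a fall shared by many subjects leaves the ratio almost unchanged. It is material only when one or two subjects have an extreme true fall. Those figures rest on four assumptions: the rule reaches AUC(0-τ) and Cmax, it is run by treatment, it is run every time, and the between-subject CV is 25 to 50%. Nothing in the SAP predicts such responders. This is something that should be changed, at low priority.

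**What to change.** - Reconcile step 2e with the preamble, for example by making exclusion permitted rather than required.
- State in 9.3.2 that the paired t-test uses all evaluable AUC(0-τ) and Cmax values. Show any result after a 3-SD exclusion beside it as a sensitivity analysis, which extends the SAP's existing two-result practice to six or more values.
- Add one sentence saying whether the test applies to PK parameters and, if so, whether to values by treatment or to subject ratios.

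The cost is SAP wording and one repeat run of the same t-test. The downside is a somewhat wider primary CI if an aberrant value is kept.

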9.3.2 Pharmacokinetic Statistical Methodology

PK parameters will be evaluated to estimate the effect of tirzepatide on the PK of OC (NGM, NGMN and EE); OC administered alone will be the reference treatment and OC coadministered with tirzepatide will be the test treatment. Log-transformed $\text{AUC}(0-\tau)$ and C_{max} of NGM, NGMN and EE will be analyzed using a paired t-test. The treatment differences between the test and reference arm will be back-transformed to present the ratio of geometric means, corresponding 90% CI, and p-value from the paired t-test.

Example SAS code:

```
proc ttest data=<data in> alpha=0.1;
  by analyte param;
  paired test*ref;
run;
```

The t_{max} will be analyzed using a Wilcoxon signed rank test for the same comparison. Estimates of the median of differences, the 90% CI for the median of differences, and p-value from the Wilcoxon signed rank test will be calculated.

The PK parameters for each treatment and analyte will be summarised and listed. Furthermore, the geometric mean and 90% CI of $AUC(0-\tau)$ and C_{max} of NGM, NGMN and EE will be plotted, along with the individual values, against treatment. For t_{max} , the median and individual values will be plotted against treatment.

9.4 Safety and Tolerability Assessments

9.4.1 Adverse Events

A pre-existing condition is defined as an adverse event (AE) that starts before the subject has provided written informed consent and is ongoing at consent. A non-treatment emergent AE is defined as an AE which starts after informed consent but prior to OC dosing in the lead-in phase. A treatment-emergent AE is defined as an AE which occurs postdose or which is present prior to dosing and becomes more severe postdose.

The assignment of TEAEs to treatments will be as follows:

- A TEAE occurring during or after Day 1 dosing in the lead-in phase and prior to tirzepatide dosing on Day 20 in Period 2 will be assigned to OC.
- A TEAE occurring during or after tirzepatide dosing on Day 20 in Period 2 will be assigned to OC + 5 mg tirzepatide SC.

Where changes in severity are recorded in the Case Report Form (CRF), each separate severity of the AE will be reported in the listings. The following rules will be applied in summary tables:

- If an AE increases in severity, the AE will only be counted once at the maximum severity with the exception of the following:
 - If an AE occurs during or after Day 1 dosing in the lead-in phase and increases in severity during or after tirzepatide dosing on Day 20 in Period 2; the AE will be counted twice (at the maximum severity for each treatment).
- If an AE decreases in severity at any time, the AE will be counted once at the maximum severity.

All AEs will be listed. Treatment-emergent AEs will be summarized by treatment (including overall), severity and relationship to the study drug. The frequency (the number of AEs, the number of subjects experiencing an AE and the percentage of subjects experiencing an AE) of treatment-emergent AEs will be summarized by treatment, Medical Dictionary for Regulatory Activities (MedDRA) version 22.1 system organ class and preferred term. The summary and frequency AE tables will be presented for all causalities and those considered related to the study drug by the investigator. Any serious AEs will be listed. AEs by day of onset will be presented.

Discontinuations due to AEs will be listed.

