5. STUDY DESIGN

This is a single-center, open-label, 2-period, fixed sequence study with a lead-in period, in healthy female subjects. Subjects may already have been on OC medication prior to screening or be OC naïve. Potential subjects will be screened to assess their eligibility to enter the study within 28 days prior to Day 1 of the lead-in period. A final follow-up visit will occur on Day 49 ± 1 day (i.e. 28 days ± 1 day after tirzepatide dosing). During each treatment period, the PK of individual components of the OC combination will be assessed on Day 21 to enable evaluation

of OC PK alone. During period 2, tirzepatide will be administered on Day 20 such that peak exposure by Day 21 (tirzepatide time of maximum observed drug concentration [t_{max}] ~ 24 hours postdose) can be attained when OC PK is evaluated on Day 21 (norgestimate [NGM] and ethinyl estradiol [EE] are rapidly absorbed after oral administration). This will permit studying the influence of tirzepatide on OC PK, in the presence of maximum exposure; i.e. with greatest impact on gastric emptying (GE).

Figure GPGR.1 illustrates the study design.

Abbreviations: Adm = admission to the clinical research unit; CRU = clinical research unit; Dis = discharge from the clinical research unit; OC = oral contraceptive; PK = pharmacokinetic

Figure GPGR.1. Illustration of study design

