9.4.5 Serum Progesterone

Compliance with the OC during the lead-in period will be assessed by serum progesterone testing on Day 21 of the lead-in period. These data will be listed.

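### Minor improvement: the by-treatment TEAE tables set at least 61 days on OC beside 28-29 days after tirzepatide and, as far as the SAP shows, give no time at risk

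*SAP*

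**What the plan says.** Section 9.4.1 of the SAP splits treatment-emergent adverse events (TEAEs) at the tirzepatide dose. An event that starts "after Day 1 dosing in the lead-in phase and prior to tirzepatide dosing on Day 20 in Period 2 will be assigned to OC". For the rest: "A TEAE occurring during or after tirzepatide dosing on Day 20 in Period 2 will be assigned to OC + 5 mg tirzepatide SC". The section gives no closing day for the second window.

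The statistics named for the frequency tables, by treatment, are "the number of AEs, the number of subjects experiencing an AE and the percentage of subjects experiencing an AE". They are produced for all causalities and again for events the investigator considers related. The section also states that "AEs by day of onset will be presented". It mentions no exposure time, subject-days or rate.

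The lengths of the windows have to be read from elsewhere:

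- Section 5: "During each treatment period, the PK of individual components of the OC combination will be assessed on Day 21".
- Section 9.4.5 places "serum progesterone testing on Day 21 of the lead-in period".
- Section 5, end of study: "A final follow-up visit will occur on Day 49 ± 1 day (i.e. 28 days ± 1 day after tirzepatide dosing").
- Section 5, prior use: "Subjects may already have been on OC medication prior to screening or be OC naïve".

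Three further sections set the context. Section 8 admits to the Safety population anyone with a dose of either product, completer or not. Section 9.4.14 rules out inferential safety analysis. Section 3 leaves the detailed table layouts to a separate shell document, which is not at hand.

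**The concern.** The OC column collects events from three consecutive stages: the lead-in, Period 1, and Period 2 up to the Day 20 dose. The OC + tirzepatide column collects events from one shorter stretch. Counts and percentages both tend to grow with the time watched. If the underlying rate of an ordinary background event were the same in both windows, the OC column would tend to show more of it. Tirzepatide coadministration would then look relatively better tolerated than it is.

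The OC column is also mixed. It includes subjects who leave before tirzepatide, and early events in women new to the OC.

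Safety and tolerability of tirzepatide given with an OC is the stated secondary objective (Section 4.2), and these tables are a main summary for it. A reader comparing the columns could miss or misjudge an excess after tirzepatide.

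**Working it through.** **Inputs from the SAP.** The lead-in has a Day 21 (Section 9.4.5). Each treatment period has its own Day 21 (Section 5). Tirzepatide is given on Day 20 of Period 2 (Sections 5 and 9.4.1). Follow-up is on Day 49 ± 1 (Section 5). About 42 subjects are enrolled so that at least 28 complete (Section 7).

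**The plan's own figure first.** Section 5 equates Day 49 with 28 days after tirzepatide dosing. From Day 20, 49 − 20 = 29; the figure 28 results from counting from Day 21 (49 − 21 = 28). The two statements differ by one day and should be reconciled. Both are carried below, with 27 to 30 days as the range over the visit window.

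**OC window.** Day numbering restarts at each stage, so a subject who reaches tirzepatide contributes at least

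- lead-in 21 + Period 1 21 + Period 2 Days 1-19 = 21 + 21 + 19 = 61 days.

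This is a lower bound, because the SAP text does not give full stage lengths. If the lead-in and Period 1 each lasted 28 days (an assumption), it would be 28 + 28 + 19 = 75 days.

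**Ratio of the windows, per subject reaching tirzepatide.**

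- 61/29 = 2.10 and 61/28 = 2.18.
- Over the visit window: 61/30 = 2.03 to 61/27 = 2.26.
- Under the 75-day assumption: 75/30 = 2.50 to 75/27 = 2.78.

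**What equal counts would mean.** Take 28 subjects who contribute both windows in full:

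- OC: 28 × 61 = 1,708 subject-days.
- OC + tirzepatide: 28 × 29 = 812 subject-days.
- For illustration, 8 events in each column: 8/1,708 = 0.47 and 8/812 = 0.99 per 100 subject-days, a ratio of 1,708/812 = 2.10.

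The ratio needs no assumed event rate; it holds for any equal counts.

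**Dropout before tirzepatide (assumed: 0 to 14 of 42, leaving evenly over the 61 days).** With 14 leaving, OC time is 28 × 61 + 14 × 30.5 = 2,135 subject-days.

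- Per subject: 2,135/42 = 50.8 days, and 50.8/29 = 1.75, down from 2.10.
- In total, which is what lies behind raw event counts: 2,135/812 = 2.63, up from 2.10.

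Dropout therefore moves the percentages and the counts in opposite directions. That is why both the number of subjects entering a window and the subject-days are needed.

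**With the lead-in shown separately.** OC alone in Periods 1 and 2 is at least 21 + 19 = 40 days: 40/29 = 1.38 and 40/28 = 1.43.

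**The case against.** The strongest reply is that the SAP contains no error here. The attribution rule is explicit, the columns are openly defined, counts and percentages by treatment are ordinary descriptive output, and no comparative safety claim or test is planned. Table rows and footnotes belong in the shells, which may already show time at risk. The day-of-onset display shows when events cluster, and the related-only tables remove events judged to be background.

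Much of this stands. It is why the point is minor, and why it falls away if the shells cover it. It does not remove the point. Columns placed side by side will be compared whether or not a test is run, and neither of the other displays, as described, carries a time denominator. The related-only tables also rest on investigator judgement in an open-label study.

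Two objections to a rate also stand. First, it spreads an early effect of a single dose over four weeks. Second, the SAP does not say whether OC is taken after Day 21 of Period 2, so the days counted are days of observation and not of OC intake. A rate would also be imprecise: for 8 and 8 events, assuming independent Poisson counts, the exact conditional 95% interval around 2.10 is about 0.69 to 6.4.

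A reader might infer more than this, in three ways the SAP does not support:

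- That the attribution rule is faulty. It is clear and consistent.
- That the OC + tirzepatide percentage is itself distorted. It describes its own window correctly; only the comparison with OC is affected.
- That the OC percentage will be inflated by a known amount. That would need a background rate and a constant hazard. The SAP gives no rate, and a constant hazard is doubtful with OC-naïve subjects in the lead-in and possible acute effects after the dose.

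**Conclusion.** The point holds as a minor, optional improvement. The two columns cover at least 61 days and 28-29 days per subject reaching tirzepatide, a ratio of about 2.1 to 2.2 (2.03 to 2.26 over the visit window), and the SAP shows no time at risk beside the counts. Equal counts from subjects contributing both windows therefore stand for about a 2.1-fold higher rate after tirzepatide.

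This rests on restarted day numbering, on each stage lasting at least to its Day 21, and on the second window ending at the follow-up visit. Longer lead-in or Period 1 stages would raise the ratio.

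The effect is confined to reading a descriptive secondary table for events with appreciable background incidence. Acute events with almost no background are best read from the day-of-onset display. The primary PK comparison is not touched.

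**What to change.** Keep all planned tables, the related-only versions and the day-of-onset display. Add to Section 9.4.1, in substance:

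- TEAEs in the lead-in will be shown separately from TEAEs on OC alone in Periods 1 and 2.
- Each column will give the number of subjects who entered that window and their subject-days of observation; TEAEs per 100 subject-days may be added.
- OC time runs from the first lead-in dose to the tirzepatide dose, or to last study contact if tirzepatide is not given, divided at the end of the lead-in. OC + 5 mg tirzepatide SC time runs from the tirzepatide dose to follow-up or last contact.
- A footnote will state that these are days of observation, not of OC intake, and that a rate averages any early post-dose effect over the whole window.

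In the same edit, reconcile Day 49 with the 28-day interval in Section 5.

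The cost is one paragraph in the SAP, matching shell rows, and programming from dosing and visit dates. The downside is a few extra rows or a column, including a lead-in category beyond the two treatments listed in Section 6. If the shells already show time at risk by column, no change to the tables is needed.
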